5.2 Secondary Endpoint

The secondary endpoint of this clinical performance study is to compare the EuGeni SARS-CoV-2 Ag RDT diagnostic accuracy (specificity and sensitivity) between the two specimen collection methods (nasopharyngeal and combined nasal mid-turbinate and throat) to assess any potential impact on diagnostic accuracy.

6. SELECTION OF SPECIMENS

6.1 Specimens and subjects providing specimens

The specimens used in this clinical performance study will be selected from any gender of subjects of the general population suspected to be infected with SARS-CoV-2 or with unknown COVID-19 status.

The Principal Investigator or designee, previously trained in this CPSP, will revise subject and specimen eligibility according to the inclusion/exclusion criteria. Those who meet all the inclusion criteria and no exclusion criteria shall be suitable to participate in the study.

6.1.1 Subject Screening

Enrolled subjects will be fully informed about the clinical performance study, following the established Informed Consent process (described in the next section). Once a duly dated and signed Informed Consent form is obtained, the clinical performance procedures may begin. Subjects under 18 years of age must be accompanied by a parent or legal representative who must also give consent for the under-age's participation in the study.

In case the subject does not meet all inclusion criteria or meets any of the exclusion criteria, the subject is considered a screening failure. The Principal Investigator or the delegated clinical performance study personnel will record the screening failure in the hospital records and on the screening log as required.

Subjects meeting general inclusion criteria and no exclusion criteria will be asked to sign an Informed Consent form if they wish to participate in the clinical performance study.

Subject data will be collected following enrollment into the clinical performance study.

6.1.2 Informed Consent

The Investigator or his/her authorized designee (if applicable) will conduct the Informed Consent process, as required by applicable regulations and the center's EC. _____

Withdrawal from the clinical performance study will not jeopardize their future medical care or relationship with the investigator.

During the discussion, the Principal Investigator or his/her authorized designee will avoid any improper influence on the subject and will respect subject's legal rights. Financial incentives will not be given to the subject. _____

The subject shall have adequate time to review, ask questions, and consider participation.

CONFIDENTIAL

If the subject agrees to participate, the Informed Consent form must be signed and dated by the subject and thereafter by the person obtaining the consent prior to any clinical performance study-specific procedures. [REDACTED]

[REDACTED]

[REDACTED]

[REDACTED]

[REDACTED]

[REDACTED]

[REDACTED]

6.1.2.1 Special Circumstances for Informed Consent

Individuals under age of 18 or under age of legal consent:

Individuals who are minors (under the age of 18 or age of legal consent, but over 12 years old) may be enrolled in this clinical performance study. Informed consent must be obtained using the IRB/EC approved informed consent in accordance with IRB/EC requirements.

In this special circumstance, the legally acceptable representative will represent the individual during the Informed Consent process, which will be performed according to the requirements in [Section 6.1.2]. The minor will also be informed about the CPS within his/her ability to understand. [REDACTED]

[REDACTED]

[REDACTED]

6.2 Eligibility Criteria

6.2.1 Inclusion Criteria

1. Specimens from subjects over 12 years old agreeing to participate in the study and with a legal representative able to provide informed consent, OR;
2. Specimens from subjects over 18 years old able to provide informed consent.
3. Specimens collected with nasopharyngeal swabs, OR;
4. Combined nasal mid-turbinate and throat specimens' collection.

6.2.2 Exclusion Criteria

1. Specimens and testing methods that are deemed not compatible with gold-standard RT-PCR standards.
2. Specimens stored for over 2 hours at 2-8 °C in between collection and testing with EuGeni SARS-CoV-2 Ag RDT
3. Specimens stored for over 5 days at -20°C between collection and testing with RT-PCR.
4. Specimens stored for over 24h at 4°C between collection and testing with RT-PCR.
5. Contamination and/or deterioration of the specimen which, in the opinion of the investigator, may affect its handling and/or analysis.
6. The subject is deemed unsuitable to participate in the study by the investigator.

CONFIDENTIAL

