4.2.1 Informed Consent and Specimen collection

Before starting any study-related activity, the subject must have provided the signed informed consent form following the requirements in [Section 6.1.2]. Next, the specimen collection will be performed by professionally trained and qualified healthcare personnel.

CONFIDENTIAL

One bilateral swab will be taken to be analyzed with the device under investigation and another bilateral swab will be taken to be analyzed with the gold-standard RT-PCR. The specimen collection method for EuGeni analysis will be performed using either a combined nasal mid-turbinate and throat swab, or a nasopharyngeal swab, which will determine the inclusion into one of the two study arms. Enrolment into the combined nasal mid-turbinate and throat arm or nasopharyngeal will not be randomized, however consecutive and parallel enrollment in both arms will take place. Regardless of the study arm, the RT-PCR specimen collection will always occur to allow result comparison between the investigational device and RT-PCR.

For further information on specimen collection, please refer to IFU [REDACTED]

[figure not shown]

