4.3 Measures Taken to Avoid and Minimize Bias

This clinical performance study has been designed to be multicenter in order to minimize bias related to site specific standard of care patient and specimen collection method.

All participants who meet the inclusion and exclusion criteria will be eligible to join the study. Inclusion into the two study arms will not be randomized, however sites will be instructed to consecutively enroll subjects into both arms. Recruitment at each investigational site will be limited to █ of the total sample size.

To avoid bias related to the collection method, all study subjects will have a bilateral swab specimen collection for investigational device analysis and for RT-PCR analysis, for direct comparison within the same subjects.

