6.3 Subject Enrolment

A subject is considered enrolled in the CPS from the moment the subject provides written informed consent and has been confirmed to meet all inclusion criteria and none of the exclusion criteria.

[REDACTED]

[REDACTED]

[REDACTED]

[REDACTED]

[REDACTED]

[REDACTED]

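### Could a collected specimen be excluded on the investigator's opinion after the test results are known?

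*Protocol*

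**What the plan says.** Criterion 5 in Protocol 6.2.2, repeated in the synopsis, excludes a specimen for "Contamination and/or deterioration of the specimen which, in the opinion of the investigator, may affect its handling and/or analysis". It gives neither an objective definition nor a time point.

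Protocol 6.1 assigns the check: "The Principal Investigator or designee, previously trained in this CPSP, will revise subject and specimen eligibility according to the inclusion/exclusion criteria". Protocol 6.1.1 describes it at subject level and before consent: "Subjects meeting general inclusion criteria and no exclusion criteria will be asked to sign an Informed Consent form". A failure there is logged: "In case the subject does not meet all inclusion criteria or meets any of the exclusion criteria, the subject is considered a screening failure". Protocol 4.2.1 puts consent ahead of collection: "Before starting any study-related activity, the subject must have provided the signed informed consent form". Protocol 6.3 counts a subject as enrolled once consent is given and the subject "has been confirmed to meet all inclusion criteria and none of the exclusion criteria"; the rest of that section is redacted.

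The other specimen criteria are storage limits. One is 2 hours at 2-8 °C before the EuGeni test. The others run up to RT-PCR: 24 hours at 4 °C, and "Specimens stored for over 5 days at -20°C between collection and testing with RT-PCR".

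SAP 2.1.1 defines the per-protocol set by eligibility and consent, and SAP 2.3.1 uses that set for the primary endpoint, each arm separately. Protocol 4.3 says the study is "designed to be multicenter in order to minimize bias related to site specific standard of care"; it also names consecutive enrolment, a recruitment cap per site and paired swabs. It does not mention masking of exclusion decisions.

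**The concern.** An opinion-based exclusion feeds the primary analysis set directly. The swab does not exist when subjects are screened, so criterion 5 can only be judged after collection. A refrigerated EuGeni swab must be tested within 2 hours, while the RT-PCR swab may wait up to 5 days frozen. A EuGeni result can therefore exist while some eligibility criteria are still open.

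The study is open-label, EuGeni results go into the case report form, and RT-PCR results go to the healthcare professionals. If a false negative were called deteriorated, or a false positive contaminated, once the results were seen, both accuracy measures would be biased upward. The one visible summary that might reveal this, protocol deviations by major and minor category (SAP 3.4), is not shown split by test result.

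**Working it through.** **Inputs.** Per arm: 300 positives, 120 hospitalized negatives and 505 negatives with respiratory symptoms (Protocol 4.1). Targets: 80% sensitivity and 98% specificity (Protocol 8.3, SAP 2.4). The stated total reproduces: 2 × (300 + 120 + 505) = 2 × 925 = 1850. Negatives per arm: 120 + 505 = 625. The error rates and decision rule behind these sizes are redacted, so the targets are treated here as point-estimate thresholds. The exclusion counts below are also assumptions.

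**Order of events.** Consent, collection and a EuGeni test within 2 hours if refrigerated, then RT-PCR within 24 hours or 5 days depending on storage. The criteria that stay open until RT-PCR are clocks and involve no opinion; that they are open says nothing about when criterion 5 is judged. Even on the literal reading of 6.3, storage eligibility closes when RT-PCR testing starts, before there is an RT-PCR result.

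**Effect on the estimates.** With n specimens, x correct results, and k excluded of which h are discordant, the estimate becomes (x − (k − h)) / (n − k).

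| Start | k | h | Estimate |
|---|---|---|---|
| Sensitivity 240/300 = 80.0% | 6 | 1.2 (unrelated to result) | 235.2/294 = 80.0% |
| same | 6 | 3 | 237/294 = 80.6% |
| same | 6 | 6 | 240/294 = 81.6% |
| Sensitivity 237/300 = 79.0% | 4 | 2 | 235/296 = 79.4% |
| same | 4 | 4 | 237/296 = 80.1% |
| Specificity 612/625 = 97.9% | 6 | 0.12 (unrelated to result) | 606.12/619 = 97.9% |
| same | 6 | 3 | 609/619 = 98.4% |
| same | 6 | 6 | 612/619 = 98.9% |

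The 95% half-widths are 1.96 × √(0.8 × 0.2/300) = 4.5 points and 1.96 × √(0.98 × 0.02/625) = 1.1 points.

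**Effect on meeting a target** (exact binomial).

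- Sensitivity, n = 300. The number of true positives needed before exclusions is 240 with none excluded, 239 with 4 excluded of which 2 are false negatives, and 237 with all 4 false negatives. At a true 79% the chance is 36.6%, 42.1% and 53.4%. At a true 85% it is 99.2%, 99.5% and 99.8%.
- Specificity, n = 625. The number of true negatives needed is 613 with none excluded, and 612 with 2 excluded of which 1 is a false positive. At a true 97.8% the chance is 38% and 49%. At a true 99% it is 98.8% and 99.5%.

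**If only the EuGeni result were known.** At the target values and the planned mix, symptomatic subjects in one arm give 300 × 0.20 = 60 false negatives and 505 × 0.98 = 494.9 true negatives. Of EuGeni-negative swabs, 60/554.9 = 10.8% are then false negatives. Discarding 6 of these swabs without the RT-PCR result removes 6 × 0.108 = 0.65 false negatives on average, so sensitivity becomes 240/299.35 = 80.2%. Material bias therefore needs knowledge of both results.

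**The case for a change.** The strongest case for a change is that the timing rule costs little to write and cannot be reconstructed reliably afterwards. Protocol 6.1, 6.1.1 and 6.2.2, where it would naturally stand, show no redaction and do not contain it. Specificity is the more exposed measure: near 98% there are only about 13 false positives among 625, so losing one or two matters. All of this stands as a description of the visible text.

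It does not establish a defect. The criterion concerns whether the specimen's condition may affect its handling or analysis, which is most naturally judged before testing. Open-label status does not show that the person judging a swab sees either result. Protocol 4.2.2 confines device results to the case report form and keeps them out of patient management. The redacted text, above all SAP 1.6, may already hold the rule.

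The obvious remedies also gain little. Flagging late judgements without saying whether those specimens stay in the per-protocol set leaves the primary estimate as it was. Naming an invalid assay as a later ground for exclusion would conflict with Protocol 2.4 and 4.2.2, which call for a repeat test.

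**Conclusion.** The observation is accurate, but it concerns a detail that is not written out in the visible text. No rule or number in the plan is wrong. Sites that apply criterion 5 as worded judge the swab on its condition before analysis, and the resulting analysis set is sound.

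The plausible effect is about 0.6 points on sensitivity (2% of positives excluded, half of them false negatives) against a half-width of 4.5 points. On specificity it is about 0.5 points (6 of 625 excluded, half of them false positives) against 1.1. Larger effects need nearly every exclusion to be discordant, and a changed pass or fail needs a true value almost at the target.

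This rests on three assumptions: 80% and 98% act as point-estimate thresholds, exclusions are few, and criterion 5 is applied in its natural sense. The documents give no exclusion rate to test the second. The redacted sections could settle the timing outright, and text missing through redaction is not a gap in the plan.

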6.3 Subject Enrolment

A subject is considered enrolled in the CPS from the moment the subject provides written informed consent and has been confirmed to meet all inclusion criteria and none of the exclusion criteria.

[REDACTED]

[REDACTED]

[REDACTED]

[REDACTED]

[REDACTED]

[REDACTED]

6.4.1 Suspension or Early Termination of the Clinical Performance Study

While no formal statistical rule for early termination of the clinical performance study for insufficient accuracy of the device under investigation is defined, the Sponsor reserves the right to discontinue the clinical performance study at any stage with suitable written notice to the investigator. Possible reason(s) may include, but are not limited to:

- Unanticipated adverse device effect (e.g., UADE) occurs and it presents an unreasonable risk to the participating subjects.
- Further product development is cancelled.

Should the clinical performance study be discontinued by the Sponsor, subjects will be followed per routine hospital practice with device-related AEs reported to the Sponsor as per vigilance/commercial reporting requirements.

[REDACTED]

7. ADVERSE EVENTS

The study has been designed to involve as little pain, discomfort, fear, and any other foreseeable risk as possible for subjects. [REDACTED]

[REDACTED]

[REDACTED]

[REDACTED]

7.1 Definition

7.1.1 Adverse Event

An adverse event (AE) is any untoward medical occurrence, unintended disease or injury, or untoward clinical signs (including abnormal laboratory findings) in subjects, users or other persons, whether or not related to the medical device under investigation.

Note 1: This definition includes events related to the medical device under investigation or the comparator.

Note 2: This definition includes events related to the procedures involved.

Note 3: For users or other persons, this definition is restricted to events related to medical devices under investigation.

7.1.2 Serious Adverse Event

If the AE meets any of the criteria below, it is regarded as a serious adverse event (SAE).

- a) Led to a death,
- b) Led to a serious deterioration in health of the subject, that either resulted in
 1. a life-threatening illness or injury, or
 2. a permanent impairment of a body structure or a body function, or
 3. in-patient hospitalization or prolongation of existing hospitalization, or
 4. medical or surgical intervention to prevent life threatening illness or injury or permanent impairment to a body structure or a body function.
 5. chronic disease
- c) Led to fetal distress, fetal death or a congenital abnormality or birth defect.

Note: A planned hospitalization for pre-existing condition, or a procedure required by the CIP, without a serious deterioration in health, is not considered to be an SAE.

7.1.3 Device Deficiency/Device Malfunction

Device deficiency is defined as an inadequacy of a medical device related to its identity, quality, durability, reliability, safety or performance, such as malfunction, misuse or use error and inadequate labeling. This includes the failure of the device to meet its performance specifications or otherwise perform as intended. Note: Performance specifications include all claims made in the labeling of the device.

CONFIDENTIAL

A device malfunction is the failure of a device to meet its performance specifications or otherwise perform as intended, when used in accordance with the instructions for use or CPSP.

7.2 Device Relationship

Determination of whether there is a reasonable possibility that an investigational product or device under investigation caused or contributed to an AE is to be performed by the Investigator and recorded on the appropriate CRF form. Determination should be based on assessment of temporal relationships, evidence of alternative etiology, medical/biologic plausibility, and patient condition (pre-existing condition).

7.2.1 Unanticipated (Serious Adverse) Device Effect [U(S)ADE]

Unanticipated serious adverse device effect (USADE) refers to any serious adverse effect on health or safety or any life-threatening problem or death caused by, or associated with, a device, if that effect, problem, or death was not previously identified in nature, severity, or degree of incidence in the investigational plan or application (including a supplementary plan or application), or any other unanticipated serious problem associated with a device that relates to the rights, safety, or welfare of subjects.

7.3.2 Unanticipated Serious Adverse Device Effect Reporting to Sponsor and EC

The Sponsor requires the Investigator to report any USADE to the Sponsor within 3 calendar days of the investigator's knowledge of the event. [REDACTED]

7.3.3 Device Deficiency/Malfunction Reporting

All device deficiencies/malfunctions should be reported on the appropriate CRF form.

The investigator should report all device deficiencies/malfunctions to the Sponsor as soon as possible but no later than outlined below.

Clinical Sites	Reporting timelines
All Sites	Device deficiencies/malfunctions must be reported to the Sponsor no later than 3 calendar days from the day the site personnel became aware of the event [REDACTED] [REDACTED] [REDACTED]

A series of seven thick black horizontal bars of varying lengths, decreasing in length from left to right. The bars are positioned in a staggered, non-linear fashion across the frame.

CONFIDENTIAL

8. **STATISTICAL CONSIDERATIONS**

8.1 **Analysis Populations**

- Arm 1, including specimens collected with nasopharyngeal swabs
- Arm 2, including specimens collected with combined nasal mid-turbinate and throat swabs

8.2 **Statistical Analyses**

8.2.1 **Primary Diagnostic Accuracy Endpoint(s) Analyses**

The evaluation of the accuracy of the EuGeni SARS-CoV-2 Ag RDT in the diagnosis of COVID-19 will be analyzed by means of the sensitivity and specificity capacity of this test.

8.2.2 Secondary Endpoint Analysis

The secondary endpoint assesses any potential impact of the specimen collection method (arms 1 and 2) on EuGeni SARS-CoV-2 Ag RDT diagnostic accuracy (specificity and sensitivity rates). [REDACTED]

8.3 Sample Size Calculation and Assumptions

The sample size calculation is based on the objective to demonstrate an 80% sensitivity and a 98% specificity of the EuGeni SARS-CoV-2 Ag RDT for COVID-19 testing, [REDACTED]

CONFIDENTIAL

A series of horizontal black bars of varying lengths, suggesting a visual representation of data or a signal. The bars are arranged vertically and have different widths, indicating different values or magnitudes.

CONFIDENTIAL

9. QUALITY CONTROL AND QUALITY ASSURANCE

9.1 Selection of Clinical Sites and Investigators

The Sponsor or designee will select investigators qualified by education, training and experience to participate in the clinical performance study. [REDACTED]

[REDACTED]

9.2 Finances and Agreements

The clinical performance study will be financed by AnteoTech., Ltd. [REDACTED]

[REDACTED]

[REDACTED]

[REDACTED]

[REDACTED]

[REDACTED]

[REDACTED]

9.4 Training

9.4.1 Site Training

All Investigators and clinical performance study personnel are required to attend Sponsor training sessions, which may be conducted at an Investigator's meeting, a site initiation visit, or other appropriate training sessions. Video call or self-training may take place as required. [REDACTED]

[REDACTED]

[REDACTED]

[REDACTED]

[REDACTED]

[REDACTED]

9.5 Monitoring

Sponsor and/or designee will monitor the clinical performance study over its duration according to the CPSP-specific monitoring plan which will include the planned extent of source data verification. This monitoring plan will be a separate document that can be updated during the course of the study.

[REDACTED]

[REDACTED]

[REDACTED]

[REDACTED]

[REDACTED]

[figure not shown]
9.6 Deviations from CPSP

The Investigator should not deviate from the CPSP for any reason except in cases of medical emergencies when the deviation is necessary to protect the rights, safety and well-being of the subject or eliminate an apparent immediate hazard to the subject. In that event, the Investigator will notify Sponsor immediately by phone or in writing.

© 2010 Pearson Education, Inc.

— 1 —

CONFIDENTIAL

CONFIDENTIAL

A series of horizontal black bars of varying lengths, likely representing redacted text or a visual effect.

10.1 Protection of Personally Identifiable Information

The Sponsor respects and protects personally identifiable information collected or maintained for this clinical performance study.

The Sponsor requires the investigational sites to transfer into Sponsor's data management systems only pseudonymous Personal Information (key-coded) necessary to conduct the clinical performance study, such as the patient's medical condition, treatment, dates of treatment, etc. [REDACTED]

The Sponsor maintains a Privacy Incident procedure that complies in all respects with Applicable Law and industry best practices.

10.2 Data Management Plan

A Data Management Plan (DMP) will describe procedures used for data entry and collection. Data review and data cleaning, and issuing, resolving data discrepancies and methods for data base lock.

CONFIDENTIAL

A large black rectangular redaction box covers the majority of the page content, starting below the header and ending above the footer. The redaction is composed of several horizontal black bars of varying lengths, creating a stepped, ladder-like appearance. There are also a few small black dots on the left side of the redaction area.

